8.4. Study Specific Adverse Events

Adverse events are common in comatose OHCA patients occurring in >90%.⁶⁴ Adverse events may be the result of the clinical context or study drug. Adverse events that meet the "serious" definition in section 8.1 will be documented and assessed using the xxxx IRB reporting criteria.

Clinical events secondary to cardiac arrest will not be reported at any grade, since these are considered symptoms of the condition being studied. These may include:

- Septic shock
- Bleeding requiring transfusion
- Bradycardia requiring pacing
- Seizure confirmed on cEEG

Study specific adverse events that are expected secondary to ceftriaxone use will be reported as required per the definitions in section 8.1 and the table below. These include:

- Clostridium difficile-associated diarrhea
- Gallbladder toxicity

• Type one hypersensitivity reactions

Study Specific Serious Adverse Events	Definition
	Unexplained and new-onset ≥3 unformed stools
Clostridium difficile-associated diarrhea	in 24 hours with a positive Clostridioides difficile
	toxin gene polymerase chain reaction assay
	Diagnosed sonographically as an echo without
Gallbladder toxicity	acoustical shadowing suggesting sludge and the
	presence of ceftriaxone-calcium salt
	Acute symptom onset (minutes to hours)
	involving the skin, mucosal tissue, or both (e.g.,
	generalized hives, pruritus or flushing, swollen
Type and hypersensitivity reactions	lips-tongue-uvula) and at least one of the
Type one hypersensitivity reactions	following (a through c):
	a. Respiratory compromise
	b. Reduced blood pressure
	c. Signs of end-organ dysfunction

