2.2. Pneumonia after Cardiac Arrest

Pneumonia is an infection of the lungs resulting in alveolar inflammation and fluid or purulent material accumulation. It is the most common infection after cardiac arrest occurring in up to 65% of patients treated with TTM.⁶ Infections are associated with increased intensive care unit (ICU) length of stay (LOS), hospital LOS, duration of mechanical ventilation, post-discharge rehabilitation need, tracheostomy, and mortality, while also reducing the incidence of a good functional outcome.⁷⁻¹¹

Pneumonia results from aspiration during cardiopulmonary resuscitation (CPR), or by introduction of oropharyngeal flora into the lungs during airway management. It may also be due to gastrointestinal hypoperfusion, which leads to ischemic injury to the intestinal mucosa, bacterial translocation, and hematogenous spread. Infection might also be the result of post-resuscitation immune suppression.¹²⁻¹⁸ The association between infection and morbidity and mortality justifies further study.

Preventing infection after OHCA may: 1) reduce exposure to broad-spectrum antibiotics and subsequent collateral damage, 2) prevent hemodynamic derangements due to local and systemic inflammation, and 3) prevent an association between infection and morbidity and mortality. These benefits must be balanced with the risk for altering bacterial resistomes in the absence of clinical infection. Accordingly, further study is warranted to understand the risk-to-benefit ratio of prophylactic antibiotics.

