3.2. Exclusion Criteria

- Name on EFIC opt-out list
- In-hospital cardiac arrest
- Interval >6 hours from ICU admission at an enrolling center to study drug initiation
- Hemoglobin less than 7.0 g/dL or requiring a transfusion
- Pregnant patients
- Preexisting terminal disease making 180-day survival unlikely
- Refused informed consent
- Emergent coronary artery bypass grafting
- Anaphylaxis or angioedema to beta-lactam antibiotics (i.e., cephalosporins or penicillins)
 - o Beta-lactam allergies listed without a known reaction will not be an exclusion
- Under legal guardianship or prisoner
- Clinical *bacterial* infection prior to hospital admission defined as any one of the following:
 - Infectious prodrome preceding OHCA
 - o Active course of antibiotics for infection prior to admission
 - o Active infection documented in the electronic medical record
 - Family or surrogate endorsement of an active infection
- Active course of antibiotics for infectious or non-infectious indications
 - A single dose of an antibiotic that is NOT ceftriaxone is acceptable prior to randomization as long as the bedside treatment team does not intend to continue the antibiotic(s)
- Indication for antibiotics at the time of screening in the opinion of the bedside treatment team
- Non-English speaking
- Goals of care are not clear at the time the screening window closes and the subject is not enrolled through the EFIC pathway
- Survival through 48 hours after ROSC is unlikely to occur

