8.3. Study Drug Discontinuation

Study drug will be discontinued if:

- 1. Gallbladder toxicity occurs OR;
- 2. Withdrawal from the trial is in the patient's best interest OR;
- 3. Infection develops warranting a change in the antibiotic regimen OR;
- 4. Subject, POAHC, or LAR declines or revokes informed consent.

In the event of stopping the study drug, patients will continue to be followed for safety and efficacy outcomes, and will collect blood, sputum, and rectal samples for the inflammation and resistome assessments.

The independent DSMB will be empowered to stop the trial for under certain circumstances:

- 1. Efficacy
 - a. The trial will not be stopped for efficacy given the intermediate outcome of interest is pneumonia, rather than death or other concrete outcomes (e.g., stroke, myocardial infarction). Additionally, it will not allow for a complete assessment of the resistome or inflammation.
- 2. Harm
 - a. There is a statistically significant increased risk for serious adverse events, including *Clostridium difficile*-associated diarrhea, gallbladder toxicity, or type one hypersensitivity reactions, during the interim analysis of the first n=60 patients enrolled. The p-value threshold for harm will be set at 0.05.
- 3. Safety
 - a. Significant safety concerns emerge and the DSMB and IRB choose to pause or stop the trial.

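### Section 8.4 exempts septic shock from adverse-event reporting with no relatedness override, so a difference between arms could be missing from the interim harm count and the safety tables

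*Combined protocol and SAP*

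**What the plan says.** Section 8.4 gives two instructions in succession. First, adverse events meeting the serious definition of 8.1 "will be documented and assessed using the xxxx IRB reporting criteria". Then: "Clinical events secondary to cardiac arrest will not be reported at any grade, since these are considered symptoms of the condition being studied". Four examples follow, introduced as events that may be included, and septic shock heads the list.

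Section 3.2 excludes patients with a clinical bacterial "infection prior to hospital admission defined as any one of the following", the criteria including "Active infection documented in the electronic medical record". It separately excludes patients with an "Indication for antibiotics at the time of screening in the opinion of the bedside treatment team".

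Section 8.3 lets the DSMB stop the trial for harm if "There is a statistically significant increased risk for serious adverse events" at the interim analysis of the first 60 patients, with a p-value threshold of 0.05. The three ceftriaxone events (*C. difficile*-associated diarrhea, gallbladder toxicity, type one hypersensitivity) are named there as included among serious adverse events, not as the whole of them.

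Section 8.1 also exempts deaths from serious-adverse-event reporting, but restores reporting when the investigator judges the death related to study drug or procedures. The exemption in 8.4 has no such clause.

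**The concern.** The reason given for the exemption is that the listed events are symptoms of the condition under study. That is a weak reason for septic shock, which is a consequence of infection, and infection is what the trial drug acts on. By the same logic pneumonia would also be secondary to the arrest, yet it is the primary outcome.

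The protocol's own text gives reasons why septic shock could differ by arm in either direction. Section 2.2 hopes prophylaxis will "prevent hemodynamic derangements due to local and systemic inflammation". Sections 2.2 and 2.5 raise altered resistomes and resistant bacteria as a risk, and 2.6 proposes an immunosuppressive effect on T cells.

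At stake is whether the unblinded DSMB at n=60, and readers of the final report, can see how many patients in each arm developed septic shock.

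**Working it through.** **The plan's own figure.** The only design calculation is 60 per arm for EOP of 55% v 30% (section 9.1). With the pooled two-sided formula, n = [1.960·√(2·0.425·0.575) + 0.842·√(0.55·0.45 + 0.30·0.70)]² / 0.25² = 60.2, so 61 per arm. Power at 60 per arm is 79.9%. It reproduces, and nothing in it depends on the exemption.

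**Is septic shock a serious event under the plan?** Section 8.1 counts life-threatening events as serious. So the first sentence of 8.4 covers septic shock, and the later sentence exempts it when it is regarded as secondary to the arrest.

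**When would cases appear?** The exclusions in 3.2 remove patients with known infection or a reason for antibiotics. New cases would therefore usually become manifest after enrolment, even where the seeding event, such as aspiration during CPR (section 2.2), came before it.

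**Where else could it be seen?**

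| Place | What it captures | Septic shock? |
|---|---|---|
| 3.11.2 secondary outcomes | Early and late pneumonia, non-pulmonary infection, ICU and hospital mortality | No |
| 3.11.3 safety outcomes, compared under 9.4 | *C. difficile* diarrhea, hypersensitivity, gallbladder disease | No |
| 6.3 ICU admission data | Shock on admission | Baseline only |
| 6.4 ICU discharge data | Infection and organism | No shock field |
| 6.5 hospital discharge data | Cause of death | Fatal cases only, as free text |
| 6, general | Information on serious adverse events | Depends on which 8.4 sentence is followed |

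Septic shock is thus outside the 9.4 comparison because it is not listed in 3.11.3. It may be outside the 8.3 count because of 8.4.

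**How much could the harm rule detect if it were counted?** With 1:1 allocation, 60 patients give about 30 per arm. If all k events fall in one of two equal arms of size n, the two-sided Fisher p-value is 2·C(n,k)/C(2n,k).

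- n=30, k=4: 2·27,405/487,635 = 0.112
- n=30, k=5: 2·142,506/5,461,512 = 0.052
- n=30, k=6: 2·593,775/50,063,860 = 0.024

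So 6 v 0 is the smallest split against zero that crosses 0.05. The same minimum of 6 v 0 applies at 60 per arm. With 3 events in one arm at n=30, 11 are needed in the other.

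The documents give no septic shock rate. Exact Fisher power under assumed rates:

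| Assumed rates | 30 per arm | 60 per arm |
|---|---|---|
| 5% v 10% | 1.9% | 8.8% |
| 10% v 20% | 9.6% | 24.7% |
| 10% v 30% | 37.2% | 73.0% |
| 20% v 40% | 29.8% | 60.0% |

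Formal detection at the interim is unlikely in every scenario. The value lies in letting the DSMB and the reader see the counts.

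**The case against.** The strongest reply is that 8.4 does not conflict with itself. Section 8.2 uses reporting to mean notifying the IRB and DSMB, while section 6 says information on serious adverse events is collected. On that reading septic shock is documented but not individually notified. This is a fair reading, and it means one cannot say the events would certainly go uncounted. But the text does not say so. It also does not say whether exempt events enter the count used in 8.3, so the ambiguity stands.

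The exemption is also conditional: it covers events secondary to the arrest, which may include septic shock. Section 8.2 separately requires notification of unexpected events reasonably or definitely related to study drug. That is a partial safeguard, but 8.4 does not say which rule prevails.

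Section 2.2 attributes infection to aspiration, bacterial translocation and post-resuscitation immune suppression, so septic shock can follow from the arrest. That stands, and the entry exclusions do not refute it. It does not make the event insensitive to treatment.

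The infections themselves are compared by arm on an intention-to-treat basis, and ICU and hospital mortality are outcomes. This also stands: what may be lost is severity, not the infections.

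Finally, the DSMB is unblinded, works under a separate charter and may act on any significant safety concern. The charter was not available for this review and might require aggregate tables. Nothing in the protocol guarantees that it does.

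**Conclusion.** The point holds as a gap in safety monitoring that is cheap to close. Under the exemption as written, a difference between arms in septic shock could be absent from the serious-adverse-event count behind the n=60 rule, and it is not among the outcomes compared under 9.4. The primary analysis and sample size are unaffected.

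The size is modest. Against zero events in one arm, 6 are needed in the other for p<0.05. Interim power is 2% to 37% under the assumed rates, none of which comes from the documents. The harm decision would therefore rarely turn on this event alone.

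Three stronger inferences are tempting and not supported:

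- A reader might conclude that the infection harm most relevant to ceftriaxone has been left out. The infection-related drug harm the protocol names is *C. difficile*-associated diarrhea, which is a safety outcome, a study-specific serious event and part of the harm rule.
- A reader might conclude that every septic shock event is discarded. Sections 6 and 8.4 both say serious events are collected or documented, so the text is unclear rather than a definite rule of omission.
- A reader might extend the point to the exempted seizures because of the excitotoxicity argument in 2.6. That section proposes a possible benefit and gives no ground for a harm signal.

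**What to change.** 1. In 8.4, state whether exempt events are still documented and whether they enter the count used for the 8.3 harm rule, so that the two sentences agree.
2. Remove septic shock from the exempt list, or add a relatedness override matching the one for deaths in 8.1. An override alone would do little. The 8.1 scale asks for at least two of three conditions: reasonable timing, no possible explanation from the patient's clinical state, and a known pattern of response. In this population the second would rarely be met.
3. Add septic shock to 6.4 beside the infection items: yes/no, date, source and organism.
4. Tabulate it by arm for the unblinded DSMB at n=60 and in the final safety report, as counts and proportions, without presenting it as a powered comparison. Expedited individual reports may stay waived.

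The cost is a wording change, a few fields taken from the chart and one table row at each look. Some attribution work is needed where post-arrest shock and sepsis overlap, and it should be done blinded to allocation.

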8.5. Management

Clostridium difficile-associated diarrhea may be treated according to the Infectious Diseases Society of America and Society for Healthcare Epidemiology of America 2017 Clinical Practice Guidelines for *Clostridium difficile* Infection in Adults and Children.⁴¹

Type one (immediate-type) hypersensitivity reactions may be managed as a medical emergency and managed according to the American Academy of Allergy, Asthma, and Immunology and American College of Allergy, Asthma, and Immunology 2020 Anaphylaxis practice parameter.⁴²

Gallbladder disease may be treated according to severity and symptoms based on hospital standards.

9. Statistical Analysis

9.1. Sample Size

Incidence of EOP without antibiotic prophylaxis is unclear due to low-quality studies, variable definitions for EOP, varying diagnostic criteria, and inconsistent reporting of antibiotic administration. Additionally, studies examine early antibiotics, which may be symptom-driven *or* prophylactic.

In the ANTHARTIC trial, the incidence of EOP at five days was 17% in the prophylaxis group and 31% in controls (absolute difference of 14%).³ When using their definition of EOP, the incidence at seven days was 19% in the prophylaxis group and 34% in controls (absolute difference of 15%).

In the TTM trial, pneumonia occurred in 52% of patients treated at 33°C and 46% in those treated at 36°C.⁶⁵ Pneumonia was not defined as early- or late-onset. In a post-hoc analysis, the incidence of pneumonia in patients admitted to centers administering antibiotic prophylaxis was 41% compared to 54% at centers that did not.⁶⁶ Clustering within centers was possible.

Using data from INTCAR, the incidence of pneumonia, which was not defined as early- or late-onset, was 33% with antibiotic prophylaxis. Accordingly, 60 patients will be randomized to each group (n=120 total). This provides 80% power at a two-tailed 5% level of significance to detect an absolute reduction in the incidence of EOP by 25%, from 55% to 30%.

9.2. Primary Efficacy Outcome

Success of randomization will be assessed by comparing baseline characteristics of patients in the drug and placebo groups, using standard descriptive statistics, means and standard deviations or medians and interquartile ranges, as appropriate for continuous variables and proportions for categorical variables. No p values will be presented as is typical in randomized trials. All data were analyzed on an intention-to-treat basis. We described the treatment effect of antibiotics on EOP using a risk ratio with 95% confidence intervals for treatment effect, and tested the effect using with the Chi-square or Fisher Exact test, the Mann-Whitney test for two independent samples, and or the Wilcoxon Signed-Ranks test for two paired samples, as appropriate. We considered two-tailed tests of significance with p<0.05 to be considered significant. All statistical analyses were performed using GraphPad Prism 8 (GraphPad Software Inc.) or SAS version 9.4 and R version 4.0.2.

9.3. Secondary Efficacy Outcomes

The secondary efficacy endpoints will be analyzed on an intention-to-treat basis. Late-onset pneumonia and other infectious outcomes will be analyzed using the same statistical approach as the primary efficacy outcome. Mortality at day 28 will be analyzed using the Chi-square test.

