3.11. Outcomes

Outcomes were developed for the present study and to help with a sample size calculation for a definitive trial powered for mortality or functional outcome. They were selected by carefully reviewing prior trials and observational data.

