6.1. Baseline Data

- Hospital
- Age (years)
- Sex (male or female as assigned at birth or in the medical record)
 - Gender cannot be reliably collected because all patients are comatose
- Height (centimeters)
- Weight (kilograms)
- Body mass index (kg/m²)
- Race
- Ethnicity
- Smoking Status
- Living environment prior to cardiac arrest
- Pre-arrest diseases
- Charlson Comorbidity Index (total)
- Modified Rankin Score
- Cerebral Performance Category (CPC) prior to cardiac arrest
- Immunosuppressive drugs prior to admission
 - o Cyclosporine
 - Tacrolimus
 - \circ Sirolimus
 - o Everolimus
 - \circ Mycophenolate
 - Enteric-coated mycophenolic acid
 - o Mizoribine
 - o Leflunomide
 - Azathioprine
 - Horse or rabbit antithymocyte globulin
 - o Muromonab-CD3
 - o Alemtuzumab
 - o Rituximab
 - o Basiliximab

- Belatacept
- o Eculizumab
- o Bortezomib
- Methotrexate
- Cyclophosphamide
- Chlorambucil
- o Tofacitinib
- o Abatacept
- o Adalimumab
- o Anakinra
- Certolizumab
- o Etanercept
- o Golimumab
- o Infliximab
- o Ixekizumab
- o Natalizumab

- o Rituximab
- o Secukinumab
- Tocilizumab
- o Ustekinumab
- Vedolizumab
- Daclizumab
- o Hydroxychloroquine
- o Sulfasalazine
- o Dapsone
- Rilonacept
- Sarilumab
- o Eculizumab
- o Belimumab
- o Brodalumab

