16.2. Modified Rankin Scale

Score	Description
0	no symptoms
1	no significant disability despite symptoms; able to carry out all usual duties and activities
2	slight disability; unable to carry out all previous activities, but able to look after own affairs without assistance
3	moderate disability; requiring some help, but able to walk without assistance
4	moderately severe disability; unable to walk without assistance and unable to attend to own bodily needs
5	severe disability; bedridden, incontinent and requiring constant nursing care and attention
6	dead

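### The comparison of good functional outcome makes no use of pre-arrest mRS and CPC, although both are collected and prior disability is not excluded; this costs precision but does not cause bias

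*Combined protocol and SAP*

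**What the plan says.** Section 3.11.2 defines good functional outcome by a fixed cut, mRS 0-3 or CPC 1-2, at hospital discharge and at six months. The definition does not refer to the patient's state before the arrest.

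Section 6.1 lists "Cerebral Performance Category (CPC) prior to cardiac arrest" and also a modified Rankin score. The Rankin line is not labelled pre-arrest, but every patient is comatose at enrolment, so no other reading makes sense.

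Sections 3.1 and 3.2 set no mRS or CPC limit. The nearest exclusion is "Preexisting terminal disease making 180-day survival unlikely", which concerns survival rather than function. Legal guardianship is also excluded and would remove some dependent patients.

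On analysis, section 9.3 states "The secondary efficacy endpoints will be analyzed on an intention-to-treat basis". It then names methods for late-onset pneumonia, other infectious outcomes and day-28 mortality, but none for functional outcome. Every test named in sections 9.2 and 9.3 is unadjusted, and baseline variables serve only a descriptive check of balance.

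Section 3.11 says the outcomes were chosen partly "to help with a sample size calculation for a definitive trial powered for mortality or functional outcome", and section 1 repeats that purpose.

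**The concern.** Appendix 16.2 describes mRS 4 as "moderately severe disability; unable to walk without assistance and unable to attend to own bodily needs". A patient in that state before the arrest, and also at CPC 3 or 4, is already beyond both cuts. Full recovery to that patient's own baseline would still be scored as failure in either arm. The data collection in sections 6.1 and 6.2 allows for such patients, since it records living environment before the arrest and offers a nursing home as an arrest location.

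These patients add outcome variance that the baseline score could explain. Randomisation is in blocks of six with no stratification stated, so neither the design nor the analysis controls their distribution between the arms. At stake is the precision of the functional comparison and the ability of whoever plans the later trial to see how much of the observed rate reflects disability that was there before the arrest.

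**Working it through.** **The plan's own figure.** Section 9.1 claims "80% power at a two-tailed 5% level of significance" with 60 per arm, for early-onset pneumonia falling from 55% to 30%. With pooled variance under the null:

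n = [1.96√(2 × 0.425 × 0.575) + 0.842√(0.55 × 0.45 + 0.30 × 0.70)]² / 0.25² = 60.2, rounded up to 61 per arm.

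Power at 60 per arm is 79.9%, so the figure reproduces. The plan gives no expected rate, sample size or power for functional outcome.

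**Inputs for the check.**
- f, the share already beyond both cuts before the arrest: not in the documents; assumed 5%, 10% and 15%, and assumed never to score good.
- Good-outcome rate among the other patients: assumed 40% vs 50%, average 45%. The 40% is anchored on two figures in the protocol: in-hospital death of 40-50% (section 8.1), and 8.5% good function out of 10.5% survival (section 2). At 50% survival this gives 0.50 × 8.5/10.5 = 40%. The 10-point effect is an assumption.
- 60 per arm (section 9.1).

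**Step 1. Dilution.** Observed rates become 0.40(1−f) and 0.50(1−f). The difference shrinks by the factor (1−f). The risk ratio stays at 0.50/0.40 = 1.25.

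**Step 2. Variance explained by belonging to the affected group.** Share = f(1−f) × 0.45² / [p(1−p)], with p = 0.45(1−f). At f = 10%: 0.0182/0.2410 = 7.6%.

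**Step 3. Chance imbalance.** SD of the between-arm difference in the affected share = √[2f(1−f)/60]. The effect on the outcome difference is 0.45 times that. At f = 10%: 5.5 points in the share and 0.45 × 5.5 = 2.5 points in the outcome.

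**Step 4. Later trial.** Sample size per arm for the diluted rates (two-sided 5%, 80% power), and the power of an all-comer trial if it were sized at 388 per arm from the unaffected subset.

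| f | Rates | Difference | Variance explained | SD, share | SD, outcome | n per arm (ratio to 388) | Power at 388 |
|---|---|---|---|---|---|---|---|
| 0 | 40.0% vs 50.0% | 10.0 | 0 | 0 | 0 | 388 (1.00) | 80% |
| 5% | 38.0% vs 47.5% | 9.5 | 4% | 4.0 | 1.8 | 425 (1.10) | 76% |
| 10% | 36.0% vs 45.0% | 9.0 | 8% | 5.5 | 2.5 | 466 (1.20) | 72% |
| 15% | 34.0% vs 42.5% | 8.5 | 11% | 6.5 | 2.9 | 512 (1.32) | 68% |

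Differences and SDs are in percentage points.

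**Step 5. Scale.** At 60 per arm and 40% vs 50%, the standard error of the difference is √(0.24/60 + 0.25/60) = 9.0 points, the 95% CI half-width is 17.7 points, and power is 19%. At f = 10% the unadjusted standard error is √(2 × 0.2410/60) = 9.0 points. Removing 7.6% of the variance gives 9.0 × √(1 − 0.076) = 8.6 points.

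**The case against.** The strongest objection is that the effect is small and its key input unknown. Functional outcome is one of many secondary outcomes, and dilution of 0.5 to 1.5 points is slight beside a CI half-width near 18 points. A nursing home in a generic list of locations says nothing about how many severely disabled patients enter. Terminal disease, guardianship, unclear goals of care and unlikely 48-hour survival may all keep the share low. The share must also count only patients beyond both cuts, because someone at mRS 4 could still be CPC 2. All of this stands, and it limits the size of the point. It does not argue against a better analysis of data already collected.

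Several stronger readings are tempting, and the documents do not support them:

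- **That the comparison is biased.** Randomisation makes the affected share equal in expectation, and its chance variation already lies inside the ordinary standard error.
- **That section 9.3 prescribes an unadjusted functional comparison.** It prescribes none. The intention-to-treat sentence is not itself wrong.
- **That every effect measure is diluted.** The risk ratio, the only measure section 9.2 names, is not.
- **That the later trial grows by 1/(1−f)², that is 1.11, 1.23 and 1.38.** That ignores the change in variance as the rates fall; on the assumed rates the factors are 1.10, 1.20 and 1.32. Nor is all of this avoidable. Restricting the endpoint to unaffected patients still means enrolling 388/(1−f) = 409, 432 and 457 per arm, so the avoidable excess is about 4%, 8% and 12%.
- **That imbalance shifts the result by 4.0 to 6.5 points.** Those are SDs of the baseline share; the SD for the outcome is 1.8 to 2.9.
- **That the later trial should be planned from the unaffected subset.** No passage says its eligibility will change. With the same patients and endpoint, the all-randomised rates are the right input, and planning from the subset would leave power at 76%, 72% or 68%.

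**Conclusion.** The point holds as one of efficiency and reporting. The plan collects the outcome's own scales before treatment, admits patients whose prior disability puts good outcome out of reach, and uses neither scale in comparing functional outcome. On assumed shares of 5-15%, with 45% good outcome among the rest, the affected group accounts for about 4-11% of outcome variance and contributes an SD of 1.8-2.9 points to the difference at 60 per arm. The absolute difference and the good-outcome rate shrink by the same 5-15%; the risk ratio is unchanged.

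These sizes rest on a share that the documents do not give, on assumed outcome rates, and on the premise that patients do not recover above their pre-arrest level. The variance figure counts only the split into affected and other patients; it does not include anything the finer grades of the scale might explain. The gain is modest and does not rescue a comparison with about 19% power for a 10-point effect.

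**What to change.** In section 9.3:

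1. Name the analysis for good functional outcome at discharge and at six months. Give the unadjusted all-randomised result, with 95% CI, as the intention-to-treat result. Beside it give an effect adjusted for pre-arrest mRS (pre-arrest CPC for the CPC version), also with 95% CI. A Mantel-Haenszel risk difference or risk ratio over pre-arrest strata would do; it keeps the effect on the planning scale and copes with a stratum that has few or no good outcomes.
2. As a supplement, report by arm the share with pre-arrest mRS 4-5 and CPC 3-4, and the good-outcome rate in the remaining patients.
3. State that the later trial will be planned from whichever estimate matches its eligibility and endpoint, and not from the subset by default.

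In section 6.1, label the Rankin line as pre-arrest.

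The cost is wording only, since both scales are already on the data collection list. The one drawback is that the supplementary rate rests on slightly fewer patients.
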